13. DEFINITION OF END OF TRIAL

13.1. End of Trial in a Member State

End of trial in a Member State of the European Union is defined as the time at which it is deemed that a sufficient number of subjects have been recruited and completed the study as stated in the regulatory application (ie, clinical trial application [CTA]) and ethics application in the Member State. Poor recruitment (recruiting less than the anticipated number in the

CTA) by a Member State is not a reason for premature termination but is considered a normal conclusion to the study in that Member State.

13.2. End of Trial in All Other Participating Countries

End of trial in all other participating countries is defined as last subject last visit (LSLV), which may be determined by the point at which the dose-escalation and study stopping rules ([Section 3.4](#)) have been met.

14. SPONSOR DISCONTINUATION CRITERIA

Premature termination of this study may occur because of a regulatory authority decision, change in opinion of the IRB/EC, or investigational product safety problems, or at the discretion of Pfizer. In addition, Pfizer retains the right to discontinue development of PF-06835375 at any time.

If a study is prematurely terminated, Pfizer will promptly notify the investigator. After notification, the investigator must contact all participating subjects and the hospital pharmacy (if applicable) within a time period set by Pfizer. As directed by Pfizer, all study materials must be collected and all CRFs completed to the greatest extent possible.

15. PUBLICATION OF STUDY RESULTS

15.1. Communication of Results by Pfizer

Pfizer fulfills its commitment to publicly disclose clinical trial results through posting the results of studies on www.clinicaltrials.gov (ClinicalTrials.gov), the European Clinical Trials Database (EudraCT), and/or www.pfizer.com, and other public registries in accordance with applicable local laws/regulations.

In all cases, study results are reported by Pfizer in an objective, accurate, balanced, and complete manner and are reported regardless of the outcome of the study or the country in which the study was conducted.

www.clinicaltrials.gov

Pfizer posts clinical trial US Basic Results on www.clinicaltrials.gov for Pfizer-sponsored interventional studies (conducted in patients) that evaluate the safety and/or efficacy of a Pfizer product, regardless of the geographical location in which the study is conducted. US Basic Results are submitted for posting within 1 year of the primary completion date (PCD) for studies in adult populations or within 6 months of the PCD for studies in pediatric populations.

PCD is defined as the date that the final subject was examined or received an intervention for the purposes of final collection of data for the primary outcome, whether the clinical study concluded according to the prespecified protocol or was terminated.

EudraCT

Pfizer posts European Union (EU) Basic Results on EudraCT for all Pfizer-sponsored interventional studies that are in scope of EU requirements. EU Basic Results are submitted for posting within 1 year of the PCD for studies in adult populations or within 6 months of the PCD for studies in pediatric populations.

www.pfizer.com

Pfizer posts Public Disclosure Synopses (clinical study report synopses in which any data that could be used to identify individual patients has been removed) on www.pfizer.com for Pfizer-sponsored interventional studies at the same time the US Basic Results document is posted to www.clinicaltrials.gov.

15.2. Publications by Investigators

Pfizer supports the exercise of academic freedom and has no objection to publication by the principal investigator (PI) of the results of the study based on information collected or generated by the PI, whether or not the results are favorable to the Pfizer product. However, to ensure against inadvertent disclosure of confidential information or unprotected inventions, the investigator will provide Pfizer an opportunity to review any proposed publication or other type of disclosure of the results of the study (collectively, “publication”) before it is submitted or otherwise disclosed.

The investigator will provide any publication to Pfizer at least 30 days before it is submitted for publication or otherwise disclosed. If any patent action is required to protect intellectual property rights, the investigator agrees to delay the disclosure for a period not to exceed an additional 60 days.

The investigator will, on request, remove any previously undisclosed confidential information before disclosure, except for any study- or Pfizer product-related information necessary to the appropriate scientific presentation or understanding of the study results.

If the study is part of a multicenter study, the investigator agrees that the first publication is to be a joint publication covering all investigator sites, and that any subsequent publications by the PI will reference that primary publication. However, if a joint manuscript has not been submitted for publication within 12 months of completion or termination of the study at all participating sites, the investigator is free to publish separately, subject to the other requirements of this section.

For all publications relating to the study, the institution will comply with recognized ethical standards concerning publications and authorship, including Section II - “Ethical Considerations in the Conduct and Reporting of Research” of the Uniform Requirements for Manuscripts Submitted to Biomedical Journals, <http://www.icmje.org/index.html#authorship>, established by the International Committee of Medical Journal Editors.

Publication of study results is also provided for in the CSA between Pfizer and the institution. In this section entitled [Publications by Investigators](#), the defined terms shall have the meanings given to them in the CSA.

If there is any conflict between the CSA and any attachments to it, the terms of the CSA control. If there is any conflict between this protocol and the CSA, this protocol will control as to any issue regarding treatment of study subjects, and the CSA will control as to all other issues.

Appendix 1. Abbreviations

The following is a list of abbreviations used in the protocol.

Abbreviation	Term
Abs	Absolute
AE	Adverse event
ACPA	Anti- Citrullinated Peptide Antibody
ACR	American College of Rheumatology
ADA	Anti-drug antibody
ADCC	Antibody-dependent cellular cytotoxicity
ALT	Alanine aminotransferase
ANA	Anti-nuclear antibodies
ANC	Absolute neutrophil count
ANCA	Anti-neutrophil cytoplasmic antibody
Anti-dsDNA	Anti-double-stranded deoxyribonucleic acid
APS	Antiphospholipid antibody syndrome
AST	Aspartate aminotransferase
AUC	Area under the curve
BA	Bioavailability
CCI	[REDACTED]
CCI	[REDACTED]
BE	Bioequivalence
β-hCG	Beta-human chorionic gonadotropin
BLyS	B Lymphocyte Stimulator
BMI	Body mass index
BP	Blood pressure
Bpm	Beats per minute
BUN	Blood urea nitrogen
Cav	Average observed concentration
CDC	Centers for Disease Control and Prevention
CK	Creatine kinase
CL	Clearance
CLIA	Clinical Laboratory Improvement Amendments
Cmax	Maximum observed concentration
CMV	Cytomegalovirus
CNS	Central nervous system
CO2	Carbon dioxide (bicarbonate)
CRF	Case report form
CRP	C-reactive protein
CRU	Clinical research unit
CSA	Clinical study agreement
csDMARDs	Conventional synthetic Disease-modifying antirheumatic drugs
CSF	Cerebrospinal fluid

Abbreviation	Term
CSR	Clinical study report
C-SSRS	The Columbia Suicide Severity Rating Scale
CT	Clinical Trial
CTA	Clinical trial application
CTCAE	Common Terminology Criteria for Adverse Events
cTfh	Circulating follicular T helper-like
CXCL13	C-X-C Motif Chemokine Ligand 13
CXCR5	C-X-C chemokine receptor type 5
DILI	Drug-induced liver injury
DMARDs	Disease-modifying antirheumatic drugs
DMC	Data monitoring committee
DNA	Deoxyribonucleic acid
CCI	[REDACTED]
DU	Disposable unit
EBV	Epstein Barr virus
EC	Ethics committee
ECG	Electrocardiogram
E-DMC	External data monitoring committee
EDP	Exposure during pregnancy
EDR	Extemporaneous dispensing record
EDTA	Edetic acid (ethylenediaminetetraacetic acid)
eGFR	Estimated Glomerular Filtration Rate
CCI	[REDACTED]
ePPND	Enhanced pre- and postnatal development study
ESR	Erythrocyte sedimentation rate
EU	European Union
EULAR	European League Against Rheumatism
EudraCT	European Clinical Trials Database
fHBP	Factor H binding protein
FIH	First in human
FSH	Follicle-stimulating hormone
GC	Germinal center
GCP	Good Clinical Practice
GCS	Global Clinical Supply
GGT	Gamma-glutamyl transferase
GLP	Good Laboratory Practice
hCG	Human chorionic gonadotropin
HepBcAb	Hepatitis B core antibody
HepBsAg	Hepatitis B surface antigen
HCV	Hepatitis C virus
HCVAb	Hepatitis C antibody
HED	Human equivalent dose

Abbreviation	Term
HIV	Human immunodeficiency virus
CCI	[REDACTED]
HSV	herpes simplex virus
ICH	International Conference on Harmonisation
ID	Identification
Ig	Immunoglobulin
IgG	Immunoglobulin G
IGRA	Interferon gamma release assay
IND	Investigational new drug application
INR	International normalized ratio
IP	Investigational product
IRB	Institutional review board
IRC	Internal review committee
IRT	Interactive response technology
ISR	Injection site reactions
IUD	Intrauterine device
IV	Intravenous
IWR	Interactive Web-based response
JCV	JC virus
CCI	[REDACTED]
LFT	Liver function test
LLN	Lower limit of normal
LSLV	Last subject last visit
mAb	Monoclonal antibody
MAD	Multiple Ascending Dose
MCH	Mean corpuscular hemoglobin
MCHC	Mean corpuscular hemoglobin concentration
MCP	Metacarpophalangeal
MCV	Mean corpuscular volume
CCI	[REDACTED]
MHP	Mental health professional
N/A	Not applicable
Nab	neutralizing antibodies
NK	Natural killer
NOAEL	No observed adverse effect level
NSAIDS	Nonsteroidal anti-inflammatory drugs
PBMCs	Peripheral blood mononuclear cells
PCD	Primary completion date
PD	Pharmacodynamic(s)
PGx	Pharmacogenomic(s)
pH	Potential of hydrogen
PI	Principal investigator

Abbreviation	Term
PIB	Powder in bottle
PIP	Proximal interphalangeal
PK	Pharmacokinetic(s)
PML	Progressive Multifocal Leukoencephalopathy
PR	Pulse rate
PT	Prothrombin time
PtGA	Patient's Global Assessment of Arthritis
QFT-G	QuantiFERON®-TB Gold In-tube test
QTc	Corrected QT
qual	Qualitative
RA	Rheumatoid arthritis
RBC	Red blood cell
RF	Rheumatoid factor
RNA	Ribonucleic acid
CCI	[REDACTED]
SAD	Single ascending dose
SAE	Serious adverse event
SAP	Statistical analysis plan
SC	Subcutaneous
SCr	Serum creatinine
SIE	Serious infectious event
CCI	[REDACTED]
SLE	Systemic lupus erythematosus
CCI	[REDACTED]
SOP	Standard operating procedure
CCI	[REDACTED]
SRSD	Single reference safety document
TB	Tuberculosis
TBili	Total bilirubin
Td	Tetanus and Diphtheria
CCI	[REDACTED]
Tfh	Follicular T helper
THC	Tetrahydrocannabinol
TK	toxicokinetics
TMCs	Tonsillar mononuclear cells
TNF	Tumor necrosis factor
ULN	Upper limit of normal
Upr/Ucr	Urinary protein to urinary creatinine ratio
US	United States
WBC	White blood cell
WNL	Within normal limits
WoCBP	Women of childbearing potential

Abbreviation	Term
WRD	Worldwide Research and Development
VAS	Visual analog scale
Vss	Volume of distribution at steady state
VZV	Varicella zoster virus

Appendix 2. List of SLE/RA-related Prohibited Medications (Immunosuppressants & Immunomodulators)

These medications are prohibited starting from specified period prior to Screening until the subject's end of study visit. If subject requires any prohibited medication during the study, the Investigator should contact sponsor medical monitor or Clinician. Subject should remain in the study and be followed per [Schedule of Activities](#) in the event of receiving a prohibited medication for disease-flare.

Drug/class	Timeframe of restriction prior to Screening
B cell depleting agents (eg, Rituximab)	52 weeks
Intravenous immunoglobulin [IVIG]	16 weeks
TNF- α inhibitors (ie, etanercept, adalimumab, infliximab) including investigational TNF- α biosimilars	8 weeks
Belimumab	12 weeks
Cyclophosphamide	24 weeks
Abatacept	8 weeks
Tofacitinib, Baricitinib or other JAK inhibitors	4 weeks
Calcineurin inhibitors (eg, cyclosporine, tacrolimus)	8 weeks
IL-6 or IL-6 receptor targeting agents (eg, sarilimab, toccilizumab)	8 weeks
Intravenous corticosteroids (ie, methylprednisolone)	8 weeks
Oral corticosteroids ^a	4 weeks
Intramuscular corticosteroids ^b	4 weeks
Any other immunosuppressant or immunomodulating drugs, including biologic and/or non-biologic therapies.	8 weeks

- a. Use of oral corticosteroids greater than prednisone 20 mg (or equivalent) is not permitted within 4 weeks of Screening. As noted in [Appendix 3](#), oral prednisone (10 mg or less) is allowed during the study, but must be at a stable dose for 4 weeks prior to Day 1.
- b. Use of intramuscular corticosteroids is not permitted within 4 weeks of screening and during the study.

Appendix 3. List of Allowed SLE/RA-related and Chronic Medications

All allowed medications must be taken as described in the table below at stable doses, defined as no more than 20% change in dose. This applies from the timeframe specified in the table until the subject's end of study visit. If subject requires any of the below medications at higher doses during the study, investigator should contact sponsor to determine if the subject should be discontinued from the study.

Only one drug from each of the classes below (immunosuppressants, anti-malarials and corticosteroids) is allowed.

Drug/class	Timeframe of restriction prior to Day 1 visit	Maximum allowed dose (stable)	Other restrictions
Immunosuppressants & Immunomodulators			
Methotrexate	8 weeks	25 mg/week	N/A
Leflunomide	8 weeks	20 mg/day	N/A
Sulfasalazine	8 weeks	3 g/day	N/A
Azathioprine	8 weeks	1 mg/kg/day	N/A
Mycophenolate	8 weeks	1.5 g/day	N/A
Anti-malarial			
Hydroxychloroquine	8 weeks	400 mg/day	Only oral formulations permitted
Chloroquine	8 weeks	250 mg/day	Only oral formulations permitted
Corticosteroids			
Oral	4 weeks	10 mg/day prednisone equivalent	N/A
Intra-articular injections	2 weeks	20 mg triamcinolone equivalent per joint	N/A
Drugs to treat chronic medical conditions			
	4 weeks	N/A	N/A

Appendix 4. Oral Corticosteroids, Systemic Equivalencies²⁵

Glucocorticoid	Equivalent Dose (mg)
Short Acting	
Cortisone	25
Hydrocortisone	20
Intermediate Acting	
Methylprednisolone	4
Prednisolone	5
Prednisone	5
Triamcinolone	4
Long Acting	
Betamethasone	0.6
Dexamethasone	0.75

Appendix 5. SLICC Classification Criteria for SLE

A subject is classified as having SLE if he or she satisfies 4 of the clinical and immunologic criteria used in the SLICC classification criteria, including at least 1 clinical criterion and 1 immunologic criterion, OR if he or she has biopsy-proven nephritis compatible with SLE in the presence of ANAs or anti-dsDNA antibodies.

The criteria do not need to be present concurrently. A criterion should only be judged as fulfilled if better explained by other causal relationships (eg, other disease, drug-site effects).²²

2012 SLICC SLE Criteria		
Clinical Criteria		
Has the subject ever experienced any of the following clinical criteria?		
1. Acute Cutaneous Lupus		
Lupus malar rash (do not count if malar discoid)	Yes	No
Bullous lupus	Yes	No
Toxic epidermal necrolysis variant of SLE	Yes	No
Maculopapular lupus rash	Yes	No
Photosensitive lupus rash in the absence of dermatomyositis	Yes	No
Subacute cutaneous lupus (nonindurated psoriasiform and/or annular polycyclic lesions that resolve without scarring, although occasionally with postinflammatory dyspigmentation or telangiectasias)	Yes	No
2. Chronic Cutaneous Lupus		
Localized classical discoid rash (above the neck)	Yes	No
Generalized classical discoid rash (above and below the neck)	Yes	No
Hypertrophic (verrucous) lupus	Yes	No
Lupus panniculitis (profundus)	Yes	No
Mucosal lupus	Yes	No
Lupus erythematosus tumidus	Yes	No
Chillblains lupus	Yes	No
Discoid lupus/lichen planus overlap	Yes	No
3. Oral or nasal ulcers in the absence of other causes, such as vasculitis, Behcet's disease/syndrome, infection (herpes), inflammatory bowel disease, reactive arthritis, and acidic foods		
Palate	Yes	No
Buccal	Yes	No
Tongue	Yes	No
Nasal	Yes	No

4. Non-scarring alopecia (diffuse thinning or hair fragility with visible broken hairs) in the absence of other causes such as alopecia areata, drugs, iron deficiency and androgenic alopecia	Yes	No
5. Synovitis involving 2 or more joints, characterized by swelling or effusion OR tenderness in 2 or more joints and thirty minutes or more of morning stiffness	Yes	No
6. Serositis		
Typical pleurisy for more than 1 day	Yes	No
Pleural effusions	Yes	No
Pleural rub	Yes	No
Typical pericardial pain (pain with recumbency improved by sitting forward) for more than 1	Yes	No
Pericardial effusion	Yes	No
Pericardial rub	Yes	No
Pericarditis by ECG in the absence of other causes, such as infection, uremia, and Dressler's pericarditis	Yes	No
7. Renal		
Urine protein/creatinine ratio (or 24 hour urine protein) representing ≥ 500 mg of protein/24hr	Yes	No
Red blood cell casts	Yes	No
8. Neurologic		
Seizures	Yes	No
Psychosis	Yes	No
Mononeuritis multiplex in the absence of other known causes such as primary vasculitis	Yes	No
Myelitis	Yes	No
Peripheral or cranial neuropathy in the absence of other known causes such as primary vasculitis, infection, and diabetes mellitus	Yes	No
Acute confusional state in the absence of other causes, including toxic-metabolic, uremia, drugs	Yes	No
9. Hemolytic anemia	Yes	No
10. Leukopenia		
Leukocytes $<4000/\text{mm}^3$ at least once in the absence of other known causes such as Felty's syndrome, drugs, and portal hypertension	Yes	No
Lymphocytes $<1000/\text{mm}^3$ at least once in the absence of other known causes such as corticosteroids, drugs and infection	Yes	No
11. Thrombocytopenia ($<100,000/\text{mm}^3$) at least once in the absence of other known causes such as drugs, portal hypertension, and thrombotic thrombocytopenic purpura (TTP)	Yes	No
Immunological criteria		
1. ANA above laboratory reference range increase	Yes	No
2. Anti-dsDNA antibody above laboratory reference range, except enzyme-linked immunosorbent assay (ELISA): twice above laboratory reference range	Yes	No
3. Anti-Sm	Yes	No

4. Antiphospholipid antibody		
Lupus anticoagulant	Yes	No
False-positive rapid plasma regain (RPR)	Yes	No
Medium or high titer anticardiolipin antibody level (IgA, IgG, or IgM)	Yes	No
Anti-β2 glycoprotein I (IgA, IgG, or IgM)	Yes	No
5. Low complement		
Low C3	Yes	No
Low C4	Yes	No
Low CH50	Yes	No
6. Direct Coombs test in the absence of hemolytic anemia	Yes	No

Appendix 6. The 2010 American College of Rheumatology/European League Against Rheumatism Classification Criteria for Rheumatoid Arthritis²¹

	Score
Target population (Who should be tested?): Patients who Have at least 1 joint with definite clinical synovitis (swelling)*	
With the synovitis not better explained by another disease†	
Classification criteria for RA (score-based algorithm: add score of categories A-D; a score of $\geq 6/10$ is needed for classification of a patient as having definite RA)‡	
Joint involvement§	
1 large joint¶	0
2-10 large joints	1
1-3 small joints (with or without involvement of large joints)#+	2
4-10 small joints (with or without involvement of large joints)	3
>10 joints (at least 1 small joint)**	5
Serology (at least 1 test result is needed for classification)††	
Negative RF and negative ACPA	0
Low-positive RF or low-positive ACPA	2
High-positive RF or high-positive ACPA	3
Acute-phase reactants (at least 1 test result is needed for classification)†††	
Normal CRP and normal ESR	0
Abnormal CRP or abnormal ESR	1
Duration of symptoms§§	
<6 weeks	0
≥ 6 weeks	1

*The criteria are aimed at classification of newly presenting patients. In addition, patients with erosive disease typical of rheumatoid arthritis (RA) with a history compatible with prior fulfillment of the 2010 criteria should be classified as having RA. Patients with longstanding disease, including those whose disease is inactive (with or without treatment) who, based on retrospectively available data, have previously fulfilled the 2010 criteria should be classified as having RA.

†Differential diagnoses vary among patients with different presentations, but may include conditions such as systemic lupus erythematosus, psoriatic arthritis, and gout. If it is unclear about the relevant differential diagnoses to consider an expert rheumatologist should be consulted.

‡Although patients with a score of $<6/10$ are not classifiable as having RA, their status can be reassessed and the criteria might be fulfilled cumulatively over time.

§Joint involvement refers to any *swollen* or *tender* joint on examination, which may be confirmed by imaging evidence of synovitis. Distal interphalangeal joints, first carpometacarpal joints, and first metatarsophalangeal joints are *excluded from assessment*. Categories of joint distribution are classified according to the location and number of involved joints, with placement into the highest category possible based on the pattern of joint involvement.

¶“Large joints” refers to shoulders, elbows, hips, knees, and ankles.

#“Small joints” refers to the metacarpophalangeal joints, proximal interphalangeal joints, second through fifth metatarsophalangeal joints, thumb interphalangeal joints, and wrists.

**In this category, at least 1 of the involved joints must be a small joint; the other joints can include any combination of large and additional small joints, as well as other joints not specifically listed elsewhere (eg, temporomandibular, acromioclavicular, sternoclavicular, etc.).

†† Negative refers to IU values that are less than or equal to the upper limit of normal (ULN) for the laboratory and assay; low-positive refers to IU values that are higher than the ULN but ≤ 3 times the ULN for the laboratory and assay; high-positive refers to IU values that are > 3 times the ULN for the laboratory and assay. Where rheumatoid factor (RF) information is only available as positive or negative, a positive result should be scored as low-positive for RF. ACPA = anti-citrullinated protein antibody.

‡‡Normal/abnormal is determined by local laboratory standards. CRP = C-reactive protein; ESR = erythrocyte sedimentation rate.

§§ Duration of symptoms refers to patient self-report of the duration of signs or symptoms of synovitis (eg, pain, swelling, tenderness) of joints that are clinically involved at the time of assessment, regardless of treatment status.

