- ee. Subjects will be continuously monitored for infusion site reactions from the start of drug administration until the end of infusion and then at time points indicated in the [Schedule of Activities](#). Infusion site reactions may be monitored beyond the time points indicated in the [Schedule of Activities](#) based on investigator's assessment.
- ff. Screening assessments may be repeated, provided this was approved by the sponsor clinician or medical monitor. Please see [Section 6.1](#) for exceptions and details on potential re-screening. Sites must obtain an approval from sponsor study clinician to proceed with screening of each subject.
- gg. SLE subjects must meet SLICC criteria described in [Appendix 5](#), RA subjects must meet 2010 ACR/EULAR criteria described in [Appendix 6](#). If subject meets criteria for both RA and SLE (note: this is relatively rare), then both SLE and RA assessments should be performed.
- hh. In order to ensure sentinel dosing is implemented, sites need to obtain written approval from the sponsor clinician to proceed with dosing of each subject in this study.

Part B (Multiple Ascending Dose)

Protocol activity	Outpatient	Inpatient		Outpatient												
		Day 1 ⁱⁱ	Day 2	Day 4	Day 8	Day 15	Day 29 ^b	Day 30 ^c	Day 36	Week 6/ Day 43	Week 8/ Day 57	Week 12/ Day 85	Week 16/ Day 113	Post- Week 16 (every 4 weeks) ^d	Post- Week 52 (every 12 weeks)	End of study visit ^e
Visit Identifier^a	Screening ^{gg}															
Visit window	-45 to -1	None		±1 day		±3 days				±7 days				±14 days		
Visit window (days)	-45 to -1	1	2	3-5	7-9	12-18	26-32	27-33	33-39	40-46	54-60	78-92	106-120	N/A	N/A	N/A
		Pre-dose	Post-dose ^f				Pre-dose	Post-dose ^f								
Enrollment Procedures																
Informed consent	X															
Inclusion/exclusion criteria	X	X														
Medical history	X															
Medication history	X															
Demography	X															
CRU confinement ^b		X	X	X												
Medical Procedures																
For all subjects																
Physical examination ^g	X	X	X	X	X	X	X	X		X	X	X	X	X	X	
Vital signs ^h	X	X	X	X	X	X	X	X		X	X	X	X	X	X	
ECG ⁱ	X	X	X	X	X	X	X	X		X	X	X	X	X	X	
Weight and height ^j	X	X												X	X ^k	
Chest X-ray ^l	X															
C-SSRS ^m	X	X					X						X			
CCI																
For subjects with RA^{hh}																
ACR/EULAR Criteria	X															
Patient's Global Assessment of Arthritis	X	X										X	X		X	
For subjects with SLE^{hh}																

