 - a. ***Rheumatoid Arthritis criteria:***
 - Confirmed diagnosis of Rheumatoid Arthritis according to the 2010 American College of Rheumatology (ACR)/European League Against Rheumatism (EULAR) criteria (See [Appendix 6](#)) at Screening, with symptom duration at least 6 months prior to Screening visit.
 - Positive with Rheumatoid Factor and/or anti-citrullinated peptide antibody (ACPA) at Screening.
 - b. ***Systemic Lupus Erythematosus (SLE) criteria:***
 - Confirmed diagnosis of SLE according to the Systemic Lupus International Collaborating Clinics (SLICC) Classification Criteria (See [Appendix 5](#)) at Screening, with symptom duration at least 6 months prior to Screening visit.
 - Positive antinuclear antibody (ANA) titer $\geq 1:80$ AND/OR positive anti-double-stranded deoxyribonucleic acid (anti-dsDNA) AND/OR anti-Smith antibodies at Screening.

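### The attribution sentence in Protocol Appendix 5 is inverted, very probably by a dropped 'not', and contradicts the SLICC items beneath it and the parallel RA rule in Appendix 6

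*Protocol*

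**What the plan says.** Protocol Section 4.1, criterion 7b, requires for the SLE group a "Confirmed diagnosis of SLE according to the Systemic Lupus International Collaborating Clinics (SLICC) Classification Criteria" and refers to Appendix 5. Footnote gg (Part A) and footnote hh (Part B) of the Schedules of Activities make the same link: "SLE subjects must meet SLICC criteria described in" Appendix 5. Section 7.8.2 repeats the counting rule (four criteria with at least one clinical and one immunologic, or biopsy-proven nephritis with ANA or anti-dsDNA) and also points to Appendix 5. It does not restate how a finding is to be attributed.

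That instruction stands only in Appendix 5, above the checklist: "A criterion should only be judged as fulfilled if better explained by other causal relationships". Other disease and drug effects are its examples of such causes.

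The items run the other way. Clinical criterion 3 reads "Oral or nasal ulcers in the absence of other causes". Criterion 4 counts alopecia "in the absence of other causes such as alopecia areata, drugs, iron deficiency and androgenic alopecia". The lymphocyte item of criterion 10 counts a low value "at least once in the absence of other known causes such as corticosteroids, drugs and infection".

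Appendix 6 gives the corresponding condition for RA: "With the synovitis not better explained by another disease".

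**The concern.** An eligibility definition should give one answer when followed. Here the general instruction asks for another cause, and many items beneath it forbid one. A site that applied both could never score those items. Where an item is silent on cause, the general instruction governs alone. Taken literally, it would credit findings due to another disease or a drug and refuse the same findings when lupus causes them.

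What is at stake is the meaning of the SLE label. The protocol's objectives are framed in subjects with SLE and RA. The SAP tabulates primary diagnosis (Section 8.3.2) and summarizes SLEDAI-2K in SLE patients (Section 8.2.1). Protocol Section 3.1 sets no minimum disease activity for entry, so attribution is not tested there either.

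**Working it through.** There is no planned figure to reproduce. The check sets the passages side by side.

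**1. Direction of each rule**

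| Place | When a finding counts |
|---|---|
| Appendix 5, sentence above the checklist | another cause explains it better |
| Appendix 5, criteria 3, 4, 10, 11 | other causes are absent |
| Appendix 6, synovitis condition | another disease does not explain it better |

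The first row stands alone against the other two.

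**2. Tally of the 11 clinical criteria in Appendix 5**

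- Qualified throughout: 3 (ulcers), 4 (alopecia), 10 (leukopenia, both items), 11 (thrombocytopenia). That is 4.
- Qualified on some sub-items: 1 (photosensitive rash, with dermatomyositis as the named alternative), 6 (ECG pericarditis, 1 of 7 items), 8 (mononeuritis, neuropathy and confusional state, 3 of 6 items). That is 3.
- No such qualifier: 2 (chronic cutaneous), 5 (synovitis), 7 (renal), 9 (hemolytic anemia). That is 4.
- Check: 4 + 3 + 4 = 11.

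Among the immunologic criteria, none is conditioned on the absence of other causes. The direct Coombs item is conditioned on the absence of hemolytic anemia, which is a different kind of condition.

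**3. Consequence by type of item**

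- Qualified items: the sentence requires another cause and the item excludes one. They cannot both be met. The item wording already blocks findings due to other causes, so these items do not over-admit.
- Unqualified items (for example synovitis, renal findings, hemolytic anemia, most serositis items, seizures, psychosis, myelitis, low complement): the inverted sentence is the only attribution rule in the appendix.

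**4. Can unqualified items alone reach the threshold?** Yes. Synovitis and hemolytic anemia (2 clinical) plus ANA and low complement (2 immunologic) make 2 + 2 = 4, with at least one of each kind. On the literal sentence, all four would count if another cause explained each better, and none would count if lupus did.

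**5. What the other entry rules catch**

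- Seropositivity at Screening (criterion 7b): can be met by ANA alone, and ANA is also the first immunologic criterion in Appendix 5. It narrows entry but does not test attribution.
- Symptom duration of at least 6 months (criterion 7b): narrows entry without addressing cause.
- Exclusion 10: removes other systemic rheumatic disease, but not drug effects or non-rheumatic causes.
- Exclusion 7: its proteinuria limb removes subjects above 1.5 g/24 h, while Appendix 5 counts proteinuria from 500 mg/24 h. Proteinuria between these values can count toward entry, and its cause then matters.

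**The case against.** The strongest reply is that no competent site would apply the sentence literally. Several items are named as forms of lupus (malar rash, bullous lupus, lupus panniculitis), and crediting those only when something else explains them better makes no sense. The same sentence contains another apparent slip, in its wording for drug effects. Criterion 7b requires a confirmed diagnosis under a named and referenced instrument, and the checklist that is actually scored shows the intended direction. This stands as an argument about likelihood: it makes actual misclassification improbable. It does not make the text consistent, and for the unqualified items nothing in the appendix gives the right direction.

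A second reply is that Appendix 5 does not act alone. That is correct. A reader might infer that it is the only gate into the SLE group, but seropositivity, symptom duration and exclusion 10 all operate independently of the disputed sentence.

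A third is that little in the analysis turns on diagnosis. RA and SLE are mixed with no minimum of either per cohort (Protocol Section 4.3), and the SAP tests no hypotheses (Section 4.1) and names no covariates (Section 6.7). This also stands, and it limits the severity. A reader might go on to infer shifts in adverse event rates or B-cell kinetics. The documents give no figure for either, and the screening B-cell floor of 80 cells/µl applies to every subject.

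**Conclusion.** The sentence is wrong as written. This is shown within the protocol alone: it contradicts the item wording in four clinical criteria throughout and in parts of three others, and it contradicts Appendix 6. It sits in an operative eligibility definition, and no passage overrides it. The most probable explanation is a lost 'not'.

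The size is modest. Sample size is unaffected, since Protocol Section 9.1 bases it on no statistical consideration. A reader might infer that the trial selected the wrong patients. That would require sites to have scored the forms literally, and nothing in the documents shows that they did. Nor does the small cohort size (3 or 6 active subjects) measure the effect: it gives the weight of any one subject, not the chance that one was misclassified.

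This is a should-fix wording correction. It assumes that the intended rule is the one the items and Appendix 6 express. How sites actually scored the unqualified items remains unknown until the forms are read.

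**What to change.** Reconcile the Appendix 5 sentence with its own items and with Appendix 6, so that a criterion is fulfilled only if it is not better explained by another cause, such as another disease or a drug side effect. Confirm the wording against the source that the appendix cites.

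Then check the recorded SLICC forms of enrolled SLE subjects. Look first at the unqualified items, and flag any subject who qualifies only under the inverted wording. SAP Section 2.1 already reports actual doses and unused cohorts, so this check is worth more than the text change. It fits the review of deviations before database closure in SAP Section 5.7. Protocol Section 9.6 treats screening data used for eligibility as source data that need not be reported, so the check may have to be made at the sites.

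Cost: a one-sentence clarification and a review of forms already collected. No new procedures, visits or subjects are needed.
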